4.4 Strategies for Recruitment and Retention

For the successful conduct and timely completion of the study, it is important that the collaborating surgeons see a high volume of patients with DD. We chose the participating surgeons as we know these practicing surgeons and their willingness to participate in the study. These practices in various cities represent the diversity of the general population in Ontario.

The surgeons involved in our study each perform LPF on an average of 60 patients per year. It is assumed that 50% of potential patients will either be ineligible or not enrolled due to refusal of consent. It is therefore anticipated that 50% of eligible patients will be recruited.

Assuming that at least 10 surgeons screen a total of 600 patients and 50% of patients screened will be enrolled it is likely that approximately 300 patients can be recruited over a 12 month period. Using the estimated sample size of 128, it is estimated that all the patients could be recruited over approximately a 6-month year period. If the actual rate of enrollment is better than predicted, the duration of patient recruitment will be shortened accordingly. If the actual rate of enrollment is worse than predicted, additional surgeons will be invited to participate in this trial.

Every reasonable effort will be made to follow all participants for the entire duration of the trial. We will collect contact information for a family member, name & address of workplace/business, email address, and any social media account details to make it easier to locate the participant. Patients will be contacted via telephone the week before each follow-up appointment as a reminder. We will try to coordinate the study-related

follow up visit with the regular clinical visit to avoid extra trips to the clinic. If this is not possible, we will provide the participants with a gift card and/or parking vouchers. Compromises will be made for participants who are unable or unwilling to come for a follow-up such as completing questionnaires via mail or email.

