6 STUDY PROCEDURES /EVALUATIONS

6.1 Schedule of Study Procedures

Patients referred to the recruiting surgeons will be screened for eligibility during their initial consultation. Patients who meet the inclusion criteria with no exclusion criteria present will be invited to join the trial and asked to provide written informed consent. Patients will be randomized after eligibility has been confirmed; it is expected that their procedure will occur 2-3 months after randomization. For the CI group, collagenase will be ordered and the procedure scheduled for as soon as possible following randomization. For the LPF group, the procedure will be done sometime in the ensuing weeks, as the procedure needs to be booked by the participating surgeon's office with the OR of the appropriate hospital. Approximately 1 week prior to their scheduled procedure, eligible, consenting patients will have their baseline data collected.

Surgeons may maintain their standard care for follow-up to patients. All patients will be seen for their study-specific follow-up visits at 1, 3, 6, and 12 months after their procedure. Best efforts will be made to coordinate routine patient care with study follow-up visits. Patients will be encouraged to contact their surgeon's office if they have any complications, questions, or concerns. If they are experiencing difficulties outside of regular hours, they will return to the emergency room of their surgeon's hospital. Patients will be asked at their follow-up visits if they have seen a physician not associated with the trial regarding their affected hand, and if so, the record will be obtained. If a patient is unable to return for follow up, copies of the quality of life questionnaires will be mailed to the patients. Reminder telephone calls will also be made to help ensure complete follow up.

If any unscheduled visits occur, the number of visits will be recorded in the patient's study diary. If occupational or physiotherapists are required to administer treatment, this information will also be recorded in the patient's study chart and in the study diary.

Additional visits for each of the study groups may occur as follows:

Collagenase Injection Group:

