7 ASSESSMENT OF SAFETY

7.1 Adverse Events

An Adverse Event (AE) is broadly defined as any untoward medical occurrence in a patient or clinical investigation occurring after the patient has signed the study consent form. The AE does not necessarily have a causal relationship with the study treatment or study procedures. Consequently, AEs include adverse drug reactions, significant abnormal laboratory values and intercurrent diseases.

AEs are expected when their nature, severity or outcome are consistent with the latest version of the Investigator's Brochure for XIAFLEX®. At each patient visit, from the date the patient provides written informed consent until the end of the study, each patient will be asked non-leading questions regarding their well-being since the last visit. Any unintended and unfavourable sign (e.g. a clinically significant abnormal laboratory finding), symptom or disease described by the patient or noted by the site staff will be recorded as an AE in the source documents, on the study CRF and followed up with more specific questions or actions as required.

If a change in the patient's health status was noted prior to drug administration, it will be recorded in the patient's source documents and in the medical, surgical or physical screening CRF pages. Only medically qualified personnel must assess AEs. For the purpose of data collection, all untoward events that occur after informed consent

through 12 months of the study period are to be recorded on the CRF by the study site. This requirement includes AEs recorded from unscheduled visits as well as scheduled visits.

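### Patients followed by mail or email are not actively asked about adverse events or outside care, so capture of both may be incomplete

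*Combined protocol and SAP*

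**What the plan says.** Section 6.1 provides for patients who cannot come to a visit: "If a patient is unable to return for follow up, copies of the quality of life questionnaires will be mailed to the patients". It continues: "Reminder telephone calls will also be made to help ensure complete follow up". Section 4.4 makes a similar offer to patients who cannot or will not attend, with the example of "completing questionnaires via mail or email". Neither section names an adverse event (AE) question, an outside-care question or return of the diary, and the calls are described only as reminders.

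Active AE questioning is tied to visits. Under 7.1, at each visit "each patient will be asked non-leading questions regarding their well-being since the last visit". The outside-care question in 6.1 works the same way: "Patients will be asked at their follow-up visits if they have seen a physician not associated with the trial" about the affected hand, and a positive answer leads to the record being obtained. The Appendix places AE monitoring at months 1, 3, 6 and 12 and at unscheduled visits.

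The recording duty is wider than this. Section 7.1 wants "all untoward events that occur after informed consent" on the CRF through month 12, and 6.3 promises AE monitoring over the whole of follow-up.

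The diary (6.2) covers health-service use, medication, expenses and time off work. Under 10.2 the research assistant extracts it to the CRF.

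**The concern.** For a patient followed by mail, no active procedure delivers the AE record that 7.1 requires. The patient returns an MHQ and looks followed at that time point, yet nobody has asked about harm or about care elsewhere.

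The comparison of harms is what is at stake. The trial is unblinded and sets an injection against surgery, and section 1.1 cites fewer serious adverse events with injection in an earlier propensity-matched study. Attendance could depend on the arm or on whether something went wrong. Complication costs also enter the economic evaluation in 6.5.

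**Working it through.** **1. The plan's own figure.** The only related number is the sample size in 8.2. With difference 8.7, SD 15.5, two-sided alpha 0.05 (two-sided is my assumption) and power 0.80, a t-based calculation needs 51 per group: power is 0.8015 at 51 and 0.7936 at 50. Allowing for 20% loss, 51 / (1 − 0.20) = 63.75, so 64 per group and 128 in total. The plan's figures reproduce, and this point does not change them. The 20% is loss to follow-up, not a share followed by mail.

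**2. Passages side by side.**

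| Route to an AE or outside care | Where | Reaches a mail-followed patient? |
|---|---|---|
| AE question | 7.1 | At visits only |
| Outside-physician question | 6.1 | At visits only |
| Look-back to the previous visit | 7.1 | Only if a later visit is attended |
| Call to the surgeon's office | 6.1 | Yes, if the patient initiates it |
| Unscheduled visit | 6.1, 7.1 | Only if the patient presents |
| Diary | 6.2, 10.2 | No return route stated; no link to the AE form |
| Contact with other providers | 4.6 | Written for withdrawal of consent |

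Every route still open to a patient who attends no later visit is passive.

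**3. Effect on a reported risk.** Let p be the true AE risk, m the share followed by mail with no later visit, and c the fraction of those patients' AEs caught by other routes. Assume that these patients have the same true risk as the others and stay in the denominator. Then:

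reported risk = p × (1 − m + m × c), so relative understatement = m × (1 − c).

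The documents give none of p, m or c, so a range is shown.

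| m | c = 0 | c = 0.5 |
|---|---|---|
| 5% | 5% | 2.5% |
| 10% | 10% | 5% |
| 20% | 20% | 10% |

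Example with an assumed p of 30% in 64 patients: 64 × 0.30 = 19.2 patients with an event. At m = 20% and c = 0, the reported risk is 0.30 × 0.80 = 24% (15.4 patients). At c = 0.5 it is 0.30 × 0.90 = 27% (17.3 patients).

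**4. Effect on the between-arm ratio.** With equal true risk in both arms, the apparent relative risk is [1 − m₂(1 − c₂)] / [1 − m₁(1 − c₁)].

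- Equal m and equal c: ratio 1, no bias.
- m of 5% and 20%, c = 0: 0.80 / 0.95 = 0.84.
- m of 10% and 20%, c = 0: 0.80 / 0.90 = 0.89.
- m of 10% and 25%, c = 0: 0.75 / 0.90 = 0.83. With c = 0.5: 0.875 / 0.95 = 0.92.

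**The case against.** A reader might infer that these patients' AEs are lost, that they are counted as event-free, and that a false relative risk near 0.83 follows. The documents do not support that reading.

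- **Not necessarily lost.** Section 6.1 encourages patients to contact the surgeon's office about complications. Section 7.1 states: "This requirement includes AEs recorded from unscheduled visits as well as scheduled visits". It also counts any symptom that the patient describes, so a complaint volunteered on a reminder call would qualify. One missed visit is covered by the look-back at the next one attended.
- **Outside care is not captured only at visits.** The diary covers it, and self-reported healthcare utilization is a secondary outcome (3.3(e)).
- **Further treatment of the digit is not ignored.** Outcome 3.3(h) covers it up to 4 years, and consent for that follow-up is taken by telephone (9.3). How those data are collected is not described.
- **No rule codes absent AE data as no event.** Section 4.6 has the CRF of a lost patient completed up to the last visit, and no AE denominator is defined.
- **The remote content may be wider than named.** In 4.4 the offer reads "such as completing questionnaires via mail or email", which is illustrative.
- **The 0.83 needs unequal assumed mail shares and no other capture.** No between-arm AE comparison is specified in section 8, and AEs are not among the outcomes in 3.2 and 3.3.

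All of this stands as a limit on the size. It does not supply an active question. A patient who attends no later visit and does not volunteer an event can still be missed, and the diary has no stated step that would bring an entry to AE assessment. Multiple imputation (8.1) is stated alongside the primary and secondary outcomes and gives no AE rule.

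**Conclusion.** The point holds in a limited form. For patients followed by mail or email, above all those who attend no later visit, AE and outside-care capture is passive and may be incomplete, while 7.1 requires complete recording through 12 months. The MHQ is among the mailed questionnaires, so the primary outcome is not affected.

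The size cannot be read from the documents. At an assumed 20% mail share, AE risk would be understated by 10% relative if half of these patients' events are caught otherwise, and by 20% if none are. This assumes that they stay in the denominator and carry the same true risk as the others. On that footing the between-arm ratio is biased only if mail share or capture differs by arm; whether either will differ is conjecture. The case for acting is that the change improves what is collected at little cost.

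**What to change.** In 6.1 and 7.1:

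1. Add to the mailed or emailed packet, or to the reminder call already planned, the same non-leading AE question, the outside-physician question, a question on further treatment of the treated digit, and return of the diary.
2. Route positive answers to medically qualified staff for the AE/SAE CRF, since 7.1 reserves AE assessment to them.
3. At central data entry (10.2), check diary entries for doctor, emergency and hospital visits against the AE CRF and query mismatches.
4. Record the mode of each contact. Report by arm and time point how many patients had active AE assessment, and treat those without it as not assessed.

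The cost is a short insert, a few minutes in a call already planned, and a data check on diaries already being extracted. The downside is small: remote AE reports are less detailed than clinic reports, which is why the mode of contact should be recorded.

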6.2 Baseline Assessment

Baseline demographic information will be collected approximately 1 week prior to the patient's procedure and will include age, height, weight, marital and employment status, income and education level, medical history and level of co-morbidities. ROM will also be collected.

In addition, 4 HRQL questionnaires will be administered at the baseline visit: MHQ, HUI3, URAM, and SDSS (see Health-related Quality of Life section below for further details). These questionnaires will be completed in the office/clinic and will take approximately 20-30 minutes to complete. The patient will also be given a diary to keep track of hospital and doctor visits, blood work, medications, and other health services related to their procedure as well as personal expenses incurred and time off from work.

6.3 Follow-up Assessment

All patients will be seen for their study-specific follow-up visits at 1, 3, 6, and 12 months after their procedure. This will involve repeat administration of the same 4 questionnaires as at the baseline assessment (MHQ, HUI3, URAM and SDSS) along with ROM assessment. Adverse events and recurrence will be monitored and documented throughout the follow-up period.

6.4 Health-related Quality of Life (HRQL)

HRQL will be assessed using the MHQ, a hand-specific outcomes instrument, at baseline and 12 months as the primary outcome measure. Secondary measures of HRQL include the HUI3, URAM and SDSS. All questionnaires will be scored using algorithms provided by the individual developers[14–17].

6.4.1 Michigan Hand Questionnaire (MHQ)

The MHQ is a thoroughly developed and sensitive hand-specific outcomes instrument which measures the health outcomes of patients with chronic hand conditions [14,20]. The MHQ contains six distinct scales: 1) overall hand function, 2) activities of daily living, 3) pain, 4) work performance, 5) aesthetics, and 6) patient satisfaction with hand function with scores ranging from 0 (poorest function) to 100 (best function). The MHQ takes approximately 15 minutes to complete and is self-administered. It can assess a patient's general hand function or if administered several times (i.e., pre- and post-operatively), it can be used to assess changes in hand function. The raw scale score

for each of the six scales is the sum of the responses of each scale item, which is converted to a score ranging from 0-100. For the pain scale, a higher score indicates more pain. For the other five scales, higher scores indicate better hand performance.

6.4.2 *Health Utilities Index Mark 3 (HUI3)*

The HUI3 is a generic multi-attribute health-status classification instrument composed of eight attributes or dimensions: vision, hearing, speech, ambulation, dexterity, emotion, cognition, and pain with five or six levels per attribute [15,21,22]. The HUI3 produces health utilities anchored at 0 for equal to being dead and 1 for perfect health. Negative scores represent states of health considered worse than being dead. The HUI3 takes approximately 10 minutes to complete and is self-administered.

6.4.3 *Unité Rhumatologique des Affections de la Main (URAM)*

The URAM is a relatively new disease-specific HRQL measure developed for DD [16] and is composed of a 9-item patient-reported questionnaire. Each item is scored between 0 and 5 depending on the difficulty in performing that particular function with total scores for DD-associated disability ranging from 0 (best) to 45 (worst). High scores suggest high levels of disability and disturbance. The URAM scale is a 1-domain outcome measure postulated to be related to disability associated with DD. The questionnaire takes approximately 1 minute to complete and is self-administered.

6.4.4 *Southampton Dupuytren's Scoring Scheme (SDSS)*

The SDSS is also a new disease-specific scoring system developed for DD with 5 domains, each relevant to DD[17] and scored on a five-point scale (no problem, mild inconvenience, modest inconvenience, definitely troublesome, severe problem). The minimum score is 0 and maximum score is 20 with higher scores suggesting higher levels of disability. The SDSS takes approximately 1 minute to complete and is self-administered.

6.5 Healthcare Resource Utilization

We will identify and tabulate the costs for the two procedures under the purview of the patient, Ministry of Health and society. We will further classify these costs into two categories: surgery-related costs and costs incurred by the patient. These valuations will be calculated for the financial year of 2015 and in Canadian dollars. The methodology used for the economic evaluation will be as per Drummond et al.[23], A methodological guide to performing cost-utility study comparing surgical techniques Can J Plast Surg 2004;12:179-187[18] and Thoma et al. Cost-Effectiveness Analysis Parallel

to a Randomized Controlled Trial Comparing Vertical Scar Reduction and Inverted T-Shaped Reduction Mammoplasty PRS 134:1093, 2014[24].

Procedural-related costs:

Pre-operative and Operative costs

The plastic surgeon's fees will be obtained from the Ministry of Health Schedule for Benefits for Physician Services (<http://www.health.gov.on.ca/en/pro/>). The anaesthesiologist's fees will be calculated based on an arithmetic sum of the costs of preoperative consultation and time in the operating room (i.e., Basic and time units used in the operating room. The time units are calculated as: time × fee per time unit). According to the Ontario Health Insurance Plan fee code, one time unit corresponds to 15 minutes of anesthesiologist time. The operating room time units for the two procedures will be obtained from the surgeon case report form respectively. The costs for the nursing staff will be based on time required in the operating room and for inpatient services.

For palmar fasciectomy the services of 2 full-time nurses are required in the operating room or 1 nurse for the Minor Procedure Room (MPR). Direct costs for the surgery, including costs for the medications, bandages, haematological investigations, etc., will be obtained from the Finance Department at St. Joseph's HealthCare, Hamilton or from other participating hospitals. The amount and type of medication required by the patient during the procedure will be obtained from each patient's anaesthesia record, and the medication costs will be determined based on the Ministry of Health's Ontario Drug Benefit Formulary/Comparative Drug Index (Available online: <https://www.healthinfo.moh.gov.on.ca/formulary/>).

Post-operative costs

Postoperative costs (post-discharge from the hospital) and costs related to complications will include the costs to visit plastic surgeon and/or other health professional (family physician), walk-in clinics and emergency room visits and will be obtained from the Ministry of Health Schedule of Benefits for Physician Services. Costs pertaining to any kind of investigation (including pathology/haematological or radiographic) and/or overnight stay at the hospital will be obtained from the Finance Department of St. Joseph's Healthcare, Hamilton or from other participating hospitals. The costs for medications will be calculated in the manner similar to that given above and will be based on each patient's post-operative note and orders. If the patient requires a visit(s) from community nurse post-surgery, the costs will be obtained from a local community nursing program.

Lost productivity costs:

The information related to the time lost from work by the patient and care-giver will be obtained from the individual patient diaries. To estimate the costs, we will use the Human Capital method (i.e. obtain average market wages for skilled workers (2015) from Statistics Canada) [23]. This statistic is equal to \$x/day and \$y on a weekly basis. We will use unskilled labour wage rates to calculate the costs related to time lost from usual or volunteering activities by the patient and the caregiver.

Costs incurred by the patient:

These expenses will include transportation-related cost (fuel and/or parking expenses, public transportation, taxi services etc. for their physician visits) and costs to hire a babysitter, housekeeper, or other services as a result of being away from home during these visits. The cost to buy hand /finger splints and out of hospital physiotherapy treatments, etc. that are not reimbursed as a part of OHIP will be included in this category. These out of pocket expenditures will be obtained from the patient diary.

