4.2 Exclusion Criteria

1. Previous treatment of the primary joint within 90 days of study inclusion
2. Patients undergoing any concomitant procedure on the same hand (e.g. carpal tunnel release, stenosing tenosynovitis release)
3. Persistent extension deficit from a previous surgery of the same digit
4. Any chronic muscular or neuromuscular disorder affecting wrist or hand
5. Patient generally unfit for surgery
6. Patient with specific treatment preference
7. Bleeding disorder or recent stroke
8. Allergy to collagenase
9. Collagenase treatment or treatment with any investigational drug within 30 days of study inclusion

10. Use of a tetracycline derivative within 14 days of first dose of study drug (because tetracycline derivatives may inhibit the collagenolytic activity of mammalian collagenase homologs [i.e., matrix metalloproteinases])
11. Pregnant or breast feeding patients
12. Patients who do not have insurance coverage for collagenase injections
13. Patients who are unable to provide informed consent or are unable to complete quality of life questionnaires due to mental capacity or neuro-psychological problems.

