5 STUDY INTERVENTIONS

5.1 Collagenase Injection (CI) Group

This procedure will be performed either in a minor procedure room or the hand clinic as per surgeon's routine practice. Collagenase will be administered with or without local anesthesia. As this is a pragmatic study we may inject more than one digit at a time just as we operate on more than one digit at a time. A recently published study by Gaston et al confirmed that two concurrent injections of CI to 2 affected joints in the same hand are generally well tolerated and the frequency of most AEs is similar to those reported in studies that use single sequential injections [19].

The patient's affected hand will be prepped with antiseptic solution. Using a hubless syringe with 0.01 mL graduations and a permanently fixed 26- or 27-gauge $\frac{1}{2}$ inch needle the required amount of reconstituted collagenase clostridium histolyticum will be withdrawn as follows: a) Cord affecting an MP joint, withdraw 0.25 mL of the reconstituted solution; b) Cord affecting a PIP joint: withdraw 0.20 mL of the reconstituted solution per published guidelines.

While applying tension to the cord in the hand to be treated, the needle will be placed into the cord while carefully ensuring that the tip stays within the cord and does not pass through the cord. After confirming the needle is placed correctly in the cord,

approximately one-third of the dose is injected. The needle tip is then withdrawn from the cord and repositioned in a slightly more distal location to the initial injection in the cord (approximately 2 to 3 mm) and another one-third of the dose is injected. Again, the needle tip is withdrawn from the cord and repositioned proximal to the initial injection (approximately 2 to 3 mm) and the final portion of the dose injected into the cord. When injecting a cord affecting the PIP joint of the fifth finger, the needle insertion should not be more than 2 to 3 mm in depth and injecting more than 4 mm distal to the palmar digital crease should be avoided.

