After the injections are completed, the patient's treated hand will be wrapped with a soft, bulky gauze dressing and kept elevated for the remainder of the day. The patient will return to the surgeon's office/clinic 1-7 days post-injection to assess if the contracture has resolved. If a contracture remains, a passive finger extension procedure, with or without local anesthesia as determined by the surgeon, will be undertaken in an attempt to disrupt the cord. If residual contracture remains the patient will return for a 30-day follow-up when the cord may be reinjected and the finger extension procedure repeated.

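### Does section 6.5 leave collagenase uncounted, or its insurer payments unplaced, so that the costing plan must change?

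*Combined protocol and SAP*

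**What the plan says.** Section 6.5 sets out the costing. For drugs used at the procedure it says: "The amount and type of medication required by the patient during the procedure will be obtained from each patient's anaesthesia record". It prices them from the Ontario drug formulary, and it also names hospital finance departments as a source of direct surgical costs, medications included. Collagenase is not named as a cost item.

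Section 5.1 describes how the drug is given: "Collagenase will be administered with or without local anesthesia", in a procedure room or clinic. The quantity is not fixed, since "we may inject more than one digit at a time" and, if contracture persists, "the patient will return for a 30-day follow-up when the cord may be reinjected".

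On who pays, exclusion 12 in section 4.2 removes "Patients who do not have insurance coverage for collagenase injections" and does not say whether the coverage is public or private. Sections 2.2 and 6.5 name three perspectives: patient, Ministry of Health and society. Section 6.5 then says: "We will further classify these costs into two categories: surgery-related costs and costs incurred by the patient". For splints, outside physiotherapy and similar items, those "that are not reimbursed as a part of OHIP will be included in this category" are patient costs, described as out of pocket and taken from the diary.

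**The concern.** Section 1.2 gives the cost of the injections as a reason for the economic question, so one expects their quantity, price and payer to be pinned down. Two things seem to be missing.

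- **Quantity.** Applied literally, the anaesthesia-record rule would miss collagenase at any session that produced no such record.
- **Payer.** Every participant has coverage for the drug, but no sentence in section 6.5 or 8.4 places an insurer's payment. If only actual Ministry payments count, drug paid for by another insurer leaves the Ministry analysis. If only out-of-pocket items count, it leaves the patient analysis too.

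The Ministry and patient results could then reflect an entry criterion and the trial's payer mix as well as the treatments. Choosing the rule after costs had been seen would invite challenge.

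**Working it through.** The plan states no figure on this point, so there is none to reproduce. The check is a reading of the sections together, followed by the arithmetic of what could be at stake.

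**1. Quantity of drug**

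- The anaesthesia-record sentence stands in a paragraph of section 6.5 that opens with nursing needs for palmar fasciectomy. It refers to each patient, but it can be read as written with surgery in mind.
- If it covers everyone, the mismatch is not confined to CI. Section 5.2 allows fasciectomy under local anaesthesia in a minor procedure room, where that record may also be absent. Another source would then be needed in both arms.
- Other sources exist. Collagenase is ordered for CI patients (section 6.1). The diary covers medications and services related to the procedure (6.2). Post-operative notes and orders are used for later medication (6.5). Case report forms are completed around any visit (10.1). The Appendix schedules in-hospital utilization at the procedure, and resource utilization at each follow-up and at unscheduled visits. Section 6.5 already draws on the surgeon's form for another quantity: "The operating room time units for the two procedures will be obtained from the surgeon case report form respectively".
- None of these is expressly said to count injections, but together they let an analyst do so.
- If a share u of sessions had no anaesthesia record and the rule were applied literally, about u of the drug cost would be missed (taking the same mean amount per session with and without a record). That would price the study drug at zero for those sessions, in a trial whose rationale cites its cost. No competent analyst would do that.

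**2. Payer**

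- Societal perspective: the drug is ordinarily counted whoever pays, so the insurer's share raises little doubt.
- Patient perspective: the items not covered by OHIP are described as out of pocket. A drug that an insurer pays for is not, so the natural reading counts only what the patient paid.
- Ministry perspective: section 2.2 names the Ministry as payer, which points to actual Ministry payments. Formulary pricing in section 6.5 could instead support charging every injection at full price. This is the one open choice.
- The two cost categories do not decide it. Section 6.5 goes on to list lost productivity under a heading of its own, so the two-way split is a loose description rather than a complete allocation rule.

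**3. Size of the Ministry choice**

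Let n be mean injections per CI patient, P the price and s the share of collagenase cost not paid by the Ministry. The two rules differ by n × P × s per CI patient. None of these inputs is in the documents. Assume n = 1.0 to 1.4, P = $500 to $2,000 and a threshold of $50,000 per QALY.

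| s | Low: 1.0 × $500 × s | High: 1.4 × $2,000 × s | QALY equivalent (gap ÷ $50,000) |
|---|---|---|---|
| 0 | $0 | $0 | 0 |
| 25% | $125 | $700 | 0.0025 to 0.014 |
| 50% | $250 | $1,400 | 0.005 to 0.028 |
| 100% | $500 | $2,800 | 0.010 to 0.056 |

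At $100,000 per QALY the last column halves. If B is CI's net monetary benefit before the drug not paid by the Ministry is charged, one rule gives B and the other B − nPs. They disagree in sign only when 0 < B < nPs. A condition of that form holds for any cost item that may be counted or left out, so it does not show that this one matters.

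**4. Direction**

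Leaving the drug out lowers CI's cost and favours CI. Treating insurer-paid drug as a patient cost, on a wide reading of the OHIP sentence, would count against CI. If coverage is public and the Ministry pays, s = 0 and the two Ministry rules agree. The direction is therefore not fixed.

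**The case for a change.** The best case for a change is that the plan leaves open how a central cost enters two of its three perspectives, and that one paragraph would close the gap before costs are seen by arm. Bootstrapping under section 8.4 would not reveal an omission, because it resamples whatever costs were entered. The factual part of this stands: section 6.5 neither names collagenase nor places an insurer's payment.

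The step to a required change does not stand. A rule charging the Ministry full price whoever paid would answer a reimbursement question. Counting actual payments is a legitimate payer analysis and fits section 2.2 at least as well, so prescribing the former replaces one defensible choice with another. Once injections are counted, both results can be computed from the drug price and a payer breakdown. Sections 6.5 and 8.4 also adopt the methods of cited costing guides, and what those say on third-party payment cannot be checked here. New form fields may come too late: sections 3.3(h) and 9.3 describe follow-up of digits already treated, so some or all procedures may be complete.

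**Conclusion.** No change to the plan follows. The quantity source is a drafting gap that analysts would fill from orders, charts and visit forms, and it can affect fasciectomy as well as CI. The payer question comes down to one choice in the Ministry perspective between two acceptable rules, and a sound report would say which was used. The size cannot be determined from the documents: under the assumed inputs it runs from $0 to $2,800 per CI patient, and it is zero if the Ministry pays for all of the drug. This conclusion assumes that records of injections given can be retrieved. The case report forms and costing guides, which were not available, may settle part of the matter. Only a secondary economic analysis is involved.
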